## Background

Total knee arthroplasty (TKA) is one of the most successful surgical procedures performed worldwide, and if conducted properly, has proven to improve pain, knee range of motion, and ultimately quality of life. Approximately 700,000 TKAs are performed annually in the United States, and this number is projected to increase to 3.48 million annually by 2030. Unfortunately, roughly 20% of patients who undergo TKA are dissatisfied with their outcome and this number has remained stagnant for the past decade. Patient satisfaction after TKA is predominantly driven by postoperative pain and function. Outcomes in TKA are influenced by multiple factors, stemming from patient-specific factors and surgically modifiable factors. Patient specific factors include body mass index (BMI), preoperative range of motion (ROM), psychological status, and other comorbidities; examples of surgically modifiable factors include the type of prosthesis utilized, posterior condylar offset, posterior tibial slope, and soft tissue balancing. Knee arthritis is a disease not only of the condylar surfaces, but of the soft tissues as well. As such, the success of a TKA depends on the ultimate restoration of the integrity of the knee articular surfaces, necessitating two critical elements, beginning with precise osteotomies and ending with soft tissue balancing to realign the lower extremity to a neutral mechanical axis. In the last three decades, this first element has been addressed by major technological advances to perform precise and reproducible osteotomies, most recently with the development of computer-assisted navigation and validation techniques and modalities that allow osteotomies based on anatomical jigs created by CT imaging of the patient's knee. Despite these advances, little advancement has been appreciated by the second element—soft tissue balancing. While precise osteotomies are critical to the success of a TKA, they do not address ligamentous stability and balance, which if absent, leads to knee instability, stiffness, accelerated prosthetic wear, aseptic loosening, and premature implant failure. Soft tissue imbalance accounts for 35% of early TKA revisions in the United States. Soft tissue balancing in TKA has traditionally been more of an art than a science, relying exclusively on the surgeon's subjective assessment based on nebulous tactile feedback after completion of the osteotomies. The diseased soft tissues (i.e. ligaments) may be lengthened, tightened, or released to achieve balance, range of motion, and functional stability. However, these methods are numerous, variable, and above all, highly subjective. The individual experience of the surgeon, including fellowship training and procedural volume play a role in their ability to balance a knee properly. Typically, it is only after many years of experience does the surgeon develop the ability to accurately assess stability in varus, valgus, anterior and posterior planes. Objective balancing of soft tissues in TKA may contribute to a decrease in pain, improve function, patient satisfaction, and ultimately decrease the rate of revision. The need for the transformation of TKA soft tissue balancing from an art to a science has been realized by a technology that allows surgeons to objectively quantify ligament balance by offering real-time, evidence-based data during TKA. The Verasense (Orthosensor Inc., Dania, FL) is a disposable wireless device embedded with force sensors and inserted into the tibial component during the trialing phase of surgery after gross balancing, allowing real-time loading values in the medial and lateral compartments of the knee and fine-tuning of the end result by further soft tissue releases to improve balance and stability. Balance in TKA is defined as stability in the sagittal plane and less than 15 pounds difference in the medial and lateral compartments of the knee. In a multi-center study, intraoperative sensors were utilized to define balance and to correlate it with improved clinical outcomes. TKAs that had undergone said balancing were compared to unbalanced TKAs, with results showing improved Knee Society Score (KSS) and Western Ontario and McMaster Universities Osteoarthritis Index (WOMAC) between balanced (172, 14.5 points) and unbalanced (145.3, 23.8 points), respectively. The authors concluded that a well-balanced TKA was the most significant contributing factor to improved postoperative outcomes. Similarly, Chow et al. investigated six-month patient-reported outcomes in a small retrospective cohort

study with short-term follow up of six months comparing sensor-assisted to non-sensor-assisted TKA balancing. They reported that the KSS, Oxford Knee Score, and knee range of motion was significantly higher in the sensor-assisted cohort and that the rate of arthrofibrosis was lower in the sensor-assisted group, however, not statistically significant. Further, Geller et al. retrospectively compared the incidence of arthrofibrosis before and after the implementation of the Verasense technology to assist with ligament balancing and reported a 5% rate of arthrofibrosis prior to implementation versus 1.6% after. In this same report, median length of surgery was 83 minutes before implementation compared to 115 minutes after. The authors reported that while the implantation of the sensor increased operative time, this additional time does not have a clinical impact and that the benefits outweigh this potential increase in operative time. Multiple reports in the literature have suggested that a well-balanced TKA, which leads to increased activity levels may be part of a cascade effect, which ultimately results in higher patient-reported outcome scores. Unfortunately, soft tissue balancing is one of the only remaining aspects of TKA that has not benefited from a consensus based on quantitative measures and objective data. As the economic environment changes in medicine, coupled with a five-fold increase in TKAs performed and the subsequent need for less experienced surgeons to perform TKAs, it is imperative that the traditional subjectivity once relied upon be replaced by more empirical and clinical data to construct a scientific consensus of what balance is. In so doing, clinical outcomes may be improved, with a resultant decrease in the rate of early revisions, and ultimately significant savings in healthcare expenditures. While the literature has demonstrated a clear advantage by technology like the Verasense, previous studies have predominantly been underpowered, with short-term follow up, and unstandardized TKAs, including surgical approach, prosthetic designs, manufacturer, and above all, not randomized and controlled.

## **Study Design**

In a randomized-controlled fashion, this investigation will evaluate the use of the Verasense technology to achieve optimal TKA balance. Patients will be randomized to either: 1) undergo manual soft tissue balancing or 2) soft tissue balancing with the Verasense. The primary outcomes of interest will include patient-reported outcomes as well knee range of motion at 3 months, 6 months, 1 year, and 2 years. Secondary outcomes of interest will include pain level as assessed by the visual analogue scale (VAS) in the acute post-operative and follow up periods, ambulation distance during inpatient physical therapy postoperatively, surgical time, tourniquet time, amount of opioid consumption, length of hospital stay, incidence of arthrofibrosis and subsequent manipulation under anesthesia. We hypothesize that the use of the Verasense technology will lead to improved soft tissue balancing in TKA and ultimately result in favorable patient-reported outcomes and postoperative knee range of motion.

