## **Statistical Procedures**

Basic statistics will be done to describe the patient demographics for the overall cohort as well as the two groups. T-test and Fischer exact test will be done to compare the two groups.

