## **Study Procedures**

Patients undergoing TKA will be randomized to receive OrthoSeonsor or surgeon-guided ligamentous balancing. Patient-reported outcomes, pain levels, range of motion will be assessed at 3 month, 6 month, 1 year, and 2 year follow up visits.

No new pre, intra, or post-operation procedures will take place if you choose to take part in this study.

Before surgery, as we do with other non-study patients, you will be asked to complete several questionnaires to evaluate the function of your knee. Also as per standard of care, your knee will be evaluated by a few brief physical exams (i.e. range of motion tests, leg stability tests, neurovascular exam).

On the day of your surgery, your TKA will be performed either with or without utilization of the OrthoSensor device. This is to be decided randomly.

As a follow-up schedule, you will be seen at three months post-operation, six months post-operation, one year post-operation, and two years post-operation, where you will repeat the standard questionnaires. You will repeat the standard physical therapy exams. These visits will include the standard of care post-operative practices, exams and questionnaires.

The information recorded at the physical exams and on the questionnaires will be viewed and used by the study team to evaluate the procedure.

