### **Research Aims and Abstracts**

Research Purpose:

The purpose of this study is to find out whether using a device to measure pressure inside a replacement knee can help the replacement knee work better long term.

Research Question(s)/Hypothesis(es):

Utilization of the OrthoSensor system will provide improved gap balancing and functional outcomes

Scientific Abstract:

It is thought that inter-compartmental soft tissue balance is an important factor with regards to primary TKA success rate. Until recently however, there has not been a way of quantifying this balance to rigorously check the validity of this correlation and determine whether ligamentous balancing

quantification improves surgical and patient-reported outcomes. Consenting patients (n=130) who present with an arthritic knee indicative of primary TKA will be randomized to undergo TKA either utilizing the OrthoSensor tibial trial device, which provides intra-operative compartmental pressure readings, or via the analogous standard of care TKA without the OrthoSensor device. Both groups will be evaluated both pre and post-operatively with various knee use scores (KSFS, WOMAC, and SF 12). The data will be analyzed to evaluate the efficacy of the OrthoSensor device and its effects on early clinical outcomes.

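### Primary outcomes are plural, unranked and set at four visits, with no lead outcome, lead visit, significance level, multiplicity control or success rule, so the false-success rate is not fixed

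*Combined protocol and SAP*

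**What the plan says.** Study Design states that the "primary outcomes of interest will include patient-reported outcomes as well knee range of motion at 3 months, 6 months, 1 year, and 2 years". It names no instrument and ranks neither the outcomes nor the visits. Its hypothesis is that the device will "ultimately result in favorable patient-reported outcomes and postoperative knee range of motion".

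Study Procedures repeats the schedule: "range of motion will be assessed at 3 month, 6 month, 1 year, and 2 year follow up visits", alongside patient-reported outcomes and pain.

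The Scientific Abstract, under Research Aims and Abstracts, says both groups are evaluated with "various knee use scores (KSFS, WOMAC, and SF 12". It does not call any of these primary.

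Statistical Procedures is the whole analysis plan. Apart from descriptive statistics it says: "T-test and Fischer exact test will be done to compare the two groups". Neither test is linked to an outcome or a visit.

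On time horizon, the Research Purpose asks whether the device "can help the replacement knee work better long term", and the Scientific Abstract speaks of "its effects on early clinical outcomes". Neither phrase designates a visit.

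**The concern.** The plan does not say which result, or which combination of results, would count as success. That rule sets the error rate of the primary analysis. Left unwritten, it can be settled after the data are seen, and a reader could not tell a planned primary result from a selected one.

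This matters more because the Study Devices section labels the study pivotal and the Scientific Abstract says the data will be used to evaluate the device's efficacy. Background also justifies the trial by weaknesses in the earlier evidence: "previous studies have predominantly been underpowered, with short-term follow up". A trial meant to improve on that evidence needs a primary result that can be recognised as such.

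**Working it through.** The documents state no error rate, so there is no figure of the plan's own to reproduce.

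**Inputs from the documents**
- Visits: 4 (3 months, 6 months, 1 year, 2 years), from Study Design and Study Procedures.
- Scores: KSFS, WOMAC and SF 12 (Scientific Abstract), plus range of motion (Study Design).

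**Assumptions not in the documents**
- The three scores are the primary patient-reported outcomes, with one test per score per visit: 4 outcomes × 4 visits = 16 tests. If only one score is primary: 2 × 4 = 8 tests.
- Two-sided level 0.05, so 0.025 in the direction favouring the device.
- Correlation of the test statistics: 0.3 to 0.9 between outcomes and 0.5 to 0.9 between visits. For a different outcome at a different visit the two values are multiplied.

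**Step 1: independent tests, as a reference only**
- Any one favourable result: 1 − 0.975^16 = 33.3%; 1 − 0.975^8 = 18.3%.
- At least one patient-reported and at least one range-of-motion result: (1 − 0.975^12)(1 − 0.975^4) = 2.5% for 16 tests; (1 − 0.975^4)² = 0.9% for 8 tests.

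Repeated measurements on the same patients will not be independent, so these are not estimates for this trial.

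**Step 2: correlated tests**

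Multivariate normal test statistics were simulated under no effect (1,000,000 draws per row). A result is favourable if z > 1.96. The rows include the corners of the assumed ranges.

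| Between outcomes / between visits | 16 tests: any one | 16 tests: both kinds | 8 tests: any one | 8 tests: both kinds |
|---|---|---|---|---|
| 0.3 / 0.5 | 24.6% | 3.0% | 14.3% | 1.3% |
| 0.3 / 0.9 | 15.5% | 1.5% | 8.7% | 0.6% |
| 0.5 / 0.7 | 18.5% | 3.3% | 11.4% | 1.7% |
| 0.8 / 0.8 | 12.1% | 4.2% | 8.6% | 2.8% |
| 0.9 / 0.5 | 13.7% | 6.5% | 10.7% | 4.9% |
| 0.9 / 0.9 | 8.4% | 3.9% | 6.5% | 2.9% |

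The both-kinds columns require at least one patient-reported and at least one range-of-motion result, each at any visit. A single pre-specified test has 2.5%.

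The two rules respond differently to correlation. The any-one rate is highest when both correlations are low. The both-kinds rate is highest when outcomes move together but visits do not, because there are then several nearly separate occasions on which both can succeed by chance.

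**Step 3: would naming only one of the two be enough?**

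Under an any-one rule:
- Visit named, four outcomes tested there: 8.8% (correlation 0.3) to 4.7% (0.9).
- Outcome named, tested at four visits: 7.8% (0.5) to 4.7% (0.9).

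Both stay above 2.5%, so the outcome and the visit both need naming.

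**Step 4: both required at the same named visit**

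Each co-primary test alone has a 2.5% favourable false-positive rate, so requiring both cannot exceed 2.5%. When neither outcome is affected, the simulated joint rate is about 0.2% at an outcome correlation of 0.3 and 1.5% at 0.9.

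**The case against.** The strongest reply is that the hypothesis joins patient-reported outcomes *and* range of motion, so success already means both. This stands only in part. The sentence states an expectation, not a decision rule, and does not say which score or visit would satisfy it. If the two results may come from different visits, Step 2 gives up to about 6.5%, some 2.6 times the single-test rate (6.5 / 2.5). At other correlations the rate falls below 2.5%. The joint wording therefore neither guarantees control nor proves inflation.

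A second reply is that the figures rest on the reviewer's choices, since the documents give no level, test count or correlations. That is correct, and the ranges are labelled accordingly. More subscales would raise the count, and a single lead score would lower it. The documentary gap does not depend on any of these figures.

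A reader might infer three stronger things that the documents do not support:
- **That the trial has a false-success rate of 8 to 25%, or 33%.** No passage adopts an any-one rule. The plan leaves the rule open, and the higher figure also needs independence between repeated measurements.
- **That the aims contradict each other on timing.** The long-term and early phrases are general statements of aim, and neither names a visit. Nor is early defined as 3 and 6 months. What stands is that the aims do not supply the missing lead visit.
- **That gated testing is the only sound remedy.** A single pre-specified longitudinal comparison across visits would also remove the multiplicity over visits, although the outcome would still have to be named.

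**Conclusion.** The point holds and should be fixed before outcome data are analysed. The primary outcomes are plural and unranked at four visits, and no lead outcome, lead visit, significance level, multiplicity control or success rule is given anywhere.

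The size depends on the unwritten rule. Under the assumptions listed in the working, a device with no effect would show at least one favourable primary result with probability of roughly 8 to 25% (16 tests) or 6 to 14% (8 tests). Requiring one result of each kind at any visit gives about 1.5 to 6.5% or 0.6 to 5%. The comparator is 2.5% for one pre-specified test. The omission itself rests on the text alone and needs none of these assumptions.

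**What to change.** Amend Study Design and Statistical Procedures before any outcome data are analysed:

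1. Name one existing outcome at one existing visit as primary, tested at two-sided 0.05. The sponsor chooses both.
2. Test range of motion at that visit next, at 0.05, only if the first test is significant. If the *and* in the hypothesis is meant literally, instead make one named score and range of motion at that same visit co-primary, with both required. If range of motion itself is chosen in item 1, the second test is a named score.
3. Label all other score-by-visit comparisons exploratory and report them with confidence intervals, or Holm-adjust them only after the primary steps have succeeded.

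With no true effect on any outcome, the chance of any false favourable claim is then at most 2.5%.

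The cost is wording; no patients, visits or data are added. Success can no longer be claimed on whichever comparison turns out positive, and in the sequential option range of motion cannot be claimed if the first test fails. Co-primaries also have less power than one primary. As an illustration only, assume a 0.5 SD effect on each outcome, 65 patients per arm (130 / 2, equal allocation assumed) and no loss. One named primary then has about 81% power, and two co-primaries about 66 to 77% for correlations of 0 to 0.9.

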## **Statistical Procedures**

Basic statistics will be done to describe the patient demographics for the overall cohort as well as the two groups. T-test and Fischer exact test will be done to compare the two groups.

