#### Lay Abstract:

In total knee replacements, it is thought that the tension on the medial compartment of the knee must be in balance with the tension on the lateral compartment of the knee for the replacement to work well and last. Until recently however, there has not been a way to test this claim with hard numbers. In this study, patients who have an arthritic knee, and are recommended to undergo total knee replacement surgery will either receive surgery using the OrthoSensor device, which provides real-time pressure readings on the compartments, or via the standard of care for total knee replacement, a procedure that solely relied on the surgeons experience and feel to balance the two compartments. By collecting quality of life, pain, and knee function information before and after surgery (at multiple post-surgery visits), efficacy of the OrthoSensor device and its effect on patients outcome will be compared.

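### The only named group comparison is a t-test or Fisher test, with no baseline adjustment and no repeated-measures model, although knee scores and range of motion are recorded before surgery and at four visits

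*Combined protocol and SAP*

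**What the plan says.** The Statistical Procedures section has two sentences. The first is descriptive: "Basic statistics will be done to describe the patient demographics for the overall cohort as well as the two groups". The second is the only between-group comparison named anywhere: "T-test and Fischer exact test will be done to compare the two groups". It does not mention an outcome, a visit, a covariate, a model for repeated measurements, a rule for missing values, or a choice between follow-up values and change from baseline.

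Other sections describe richer data:

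- Research Aims and Abstracts (Scientific Abstract): "Both groups will be evaluated both pre and post-operatively with various knee use scores (KSFS, WOMAC, and SF 12").
- Study Procedures, before surgery: "your knee will be evaluated by a few brief physical exams (i.e. range of motion tests, leg stability tests, neurovascular exam").
- Study Procedures, after surgery: "Patient-reported outcomes, pain levels, range of motion will be assessed at 3 month, 6 month, 1 year, and 2 year follow up visits".
- Study Design makes patient-reported outcomes primary, together with "knee range of motion at 3 months, 6 months, 1 year, and 2 years". No single visit is chosen.
- Background, on what influences outcome: "Patient specific factors include body mass index (BMI), preoperative range of motion (ROM), psychological status, and other comorbidities".

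The planned number of patients is 130. No allocation ratio, significance level, power, effect size, SD or dropout rate is given.

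**The concern.** The trial measures each main outcome once before surgery and four times after it, and its own Background names one of those baseline measures (range of motion) as a factor in outcome. The stated analysis gives none of this a role. A t-test on follow-up values ignores baseline. A t-test on change scores uses baseline, but with a fixed coefficient of 1 instead of the coefficient the data support. Done visit by visit, either test uses only patients with a value at that visit.

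Two things are at stake. The first is precision in a sample of 130. The second is the behaviour of the comparison when patients miss visits, most plausibly at 2 years: comparing attendees can be biased if the reasons for absence relate to outcome differently in the two arms.

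The sentence follows one about demographics, so it may refer to patient characteristics only. On that reading no outcome analysis is specified at all, and the same change fills the gap.

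**Working it through.** **Inputs.** From the documents: 130 patients, two arms, one pre-operative and four post-operative measurements. Assumed, because the documents are silent: 1:1 allocation (65 per arm), two-sided 0.05, a true difference of 0.5 SD, equal SD at baseline and follow-up, complete follow-up for the power figures, and baseline-outcome correlation r of 0.3, 0.4 or 0.5. The figure of 130 has no stated derivation, so there is no plan figure to reproduce.

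**Step 1: variance relative to a follow-up t-test.**

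- Change score: 2(1 − r) = 1.40, 1.20, 1.00.
- Baseline-adjusted: 1 − r² = 0.91, 0.84, 0.75.
- Adjusted against change score: (1 − r²) / [2(1 − r)] = (1 + r)/2 = 0.65, 0.70, 0.75.

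Adjustment therefore cuts variance by 9%, 16% and 25% against the follow-up t-test, and by 35%, 30% and 25% against the change-score t-test.

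**Step 2: power.** The noncentrality is 0.5 / √(f × 2/65), with f the variance factor above. For f = 1 this is 0.5 / 0.1754 = 2.85. Noncentral-t results:

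| Analysis | r = 0.3 | r = 0.4 | r = 0.5 |
|---|---|---|---|
| Follow-up t-test | 80.8% | 80.8% | 80.8% |
| Change-score t-test | 66.7% | 73.3% | 80.8% |
| Baseline-adjusted | 84.3% | 87.0% | 90.4% |

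With 2:1 allocation (87 and 43) the follow-up test has 75.9%, the change score 61.4%, 68.1% and 75.9%, and the adjusted analysis 79.7%, 82.8% and 86.7%.

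The smallest effect detectable with 80% power at 65 per arm is 0.495 SD for the follow-up t-test, 0.586, 0.542 and 0.495 SD for change scores, and 0.472, 0.454 and 0.429 SD with adjustment.

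**Step 3: missing visits.** Further assumptions: 25% missing at 2 years, log-odds of missing changing by 1 per SD of the 1-year score, correlation 0.6 between visits and 0.4 with baseline. Large-sample simulation with 1,000,000 patients per arm gives this bias in the 2-year t-test on attendees:

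| Missingness pattern | 25% missing | 10% missing |
|---|---|---|
| Same rule in both arms | 0.00 to −0.03 SD | 0.00 to −0.02 SD |
| Depends on score in one arm only | 0.13 SD | 0.06 SD |
| Opposite patterns in the two arms | 0.25 SD | 0.11 SD |

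In the first row the two ends are for no effect and for a true 0.5 SD effect. For visit correlations of 0.5 to 0.7 at 25% missing, the second row ranges from 0.105 to 0.146 SD and the third from 0.213 to 0.299 SD. Adjusting for baseline at that visit alone still leaves 0.095 and 0.189 SD. A model that also uses the earlier visits brings the bias to about zero, but by construction, because dropout was generated from the observed 1-year score.

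**Step 4: trial-sized check.** 2,500 simulated trials, 65 per arm, 5% of baselines missing and mean-imputed, 25% missing at 2 years at random. The SD of the 2-year estimate is 0.205 (t-test), 0.190 (visit-wise adjustment) and 0.181 (repeated-measures model). That is a variance reduction of about 13% and 22%, subject to a few points of simulation error.

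**The case against.** The strongest reply is that the criticised analysis is valid. Randomisation makes an unadjusted t-test unbiased with complete follow-up, so the gain is efficiency only, and its size depends on a correlation the documents do not give. At r = 0.1 or 0.2 the adjusted power is 81.1% or 82.3% against 80.8%, which is negligible; at r = 0.6 it is 94%. This stands as a limit on how precisely the gain can be sized. It does not change the direction: at zero correlation adjustment costs about one degree of freedom.

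Chance baseline imbalance is also not a second harm. It is the same precision loss seen from within one realised allocation. This stands, and it is not counted separately here.

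The larger attrition biases need missingness that depends on outcome differently by arm, and nothing in the documents predicts that. This stands too: under a common rule the bias is close to zero, so these figures show what could happen and are not a forecast. Without that mechanism, the case for the mixed model over simple baseline adjustment rests on the 22% against 13% variance reduction and on having a defined use of all four visits.

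Finally, the defect could be called under-specification, not a wrong test, since change scores are never mentioned. But the open choice has consequences: at r = 0.3 the same data could be analysed with 67% or 84% power.

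**Conclusion.** The concern holds. The plan names two simple tests and gives no role to baseline values or repeated visits that it already collects. Under the stated assumptions, baseline adjustment raises power for a 0.5 SD effect by about 3 to 10 percentage points over a follow-up t-test (84.3 − 80.8 = 3.5 at r = 0.3; 90.4 − 80.8 = 9.6 at r = 0.5). Over a change-score t-test the gain is about 10 to 18 points (90.4 − 80.8 = 9.6; 84.3 − 66.7 = 17.6). Bias from missing visits ranges from near zero to 0.25 SD at 25% missing, depending on a mechanism that cannot be known in advance. A repeated-measures model protects against it only so far as observed scores explain the missingness.

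This should be changed, but it does not invalidate the trial as planned. Confidence in the facts is high. Confidence in the size is moderate, because every correlation, effect and dropout figure is assumed.

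**What to change.** In Statistical Procedures, replace the t-test for KSFS, WOMAC, SF 12 and range of motion with wording such as:

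> Each outcome will be analysed by a linear mixed model for repeated measures with arm, visit, arm-by-visit, baseline value and baseline-by-visit as fixed effects and an unstructured covariance. All randomised patients with any post-operative value are included in their randomised arm. A missing baseline is replaced by the mean baseline of all patients. If the model does not converge, a heterogeneous compound-symmetry covariance is used. The arm difference with 95% confidence interval is reported at 3 months, 6 months, 1 year and 2 years.

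The fallback covariance is named so that no choice remains after the data are seen; another simple heterogeneous structure would also serve.

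Alongside this:

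- Choose one primary visit. Study Design lists all four as primary; the model estimate at the chosen visit then becomes the primary comparison.
- Treat follow-up VAS pain the same way, with a baseline term only if a pre-operative VAS is recorded. The Lay Abstract refers to pain before surgery only in general terms ("By collecting quality of life, pain, and knee function information before and after surgery"). If there is none, omit that term.
- Keep two-group tests for outcomes without a baseline (surgical time, tourniquet time, length of stay) and say that ambulation distance, opioid consumption and acute post-operative VAS stay under them too. Keep Fisher's exact test for arthrofibrosis and manipulation under anesthesia.

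The cost is new wording in the analysis section, slightly more programming and a check on pre-operative VAS. The data for the four main outcomes are already collected, so no visits or patients are added.
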